5.8.1 Sample Size

At the participating hospital (Hospital Universitario de la Princesa), cardiac surgery provides a continuous daily flow of patients (one or two per day) who could potentially become candidates for the study if they meet inclusion criteria and not exclusion criteria. Assuming a 15% improvement in right ventricular function measured by echocardiographic parameters in response to iNO or pulmonary recruitment (9) and a confidence level of 95%, the estimated sample size will be 54 patients, 18 in each group (27 per center). However, due to the lack of

Versión 2: September 1, 2023

sufficient studies analyzing right ventricular response to iNO, RM, or both, the final sample size may be adjusted based on preliminary results from initial pilot patients and study progress.

5.8.2 Statistical Methods

Variables will undergo descriptive analysis of central tendency measures including mean, median, dispersion, standard deviation, and interquartile range, respectively. Homoscedasticity and normality assumptions will be confirmed using Levene's and Shapiro-Wilk tests, respectively.

Variables with normal distribution and similar variance will be compared using the t-test, and variables with non-normal distribution using the non-parametric Wilcoxon test. Pearson's chi-squared test will be used for categorical variables to compare groups at the three measurement points in the study, and Fisher's exact test when expected frequencies are < 5 .

For the comparison of more than two means with homoscedastic variances and normal distribution, ANOVA with post hoc testing will be conducted. For variables with heteroscedastic variances and/or non-normal distribution, the Kruskal-Wallis post hoc test will be applied. To analyze temporal evolution, a repeated measures ANOVA will be used with the intervention type as the main factor. In case of non-normality, the non-parametric Friedman test will be applied. Statistical significance will be set at $p \leq 0.05$. Statistical analysis will be performed using Stata v.15.

6. Safety and Adverse Events

To ensure safety during the 2-hour duration of the research protocol, the following precautions will be taken:

The inclusion of unstable patients or those who have had significant intraoperative complications leading to instability will be avoided.

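### Pre-tests on the trial data choose the analysis of each primary variable, and a failed normality check swaps the repeated-measures analysis by arm for a test that does not compare the arms

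*Protocol*

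**What the plan says.** Protocol section 5.8.2 sets the checks: "Homoscedasticity and normality assumptions will be confirmed using" the Levene test for variances and the Shapiro-Wilk test for normality. Three choices hang on them.

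- **Two groups:** "Variables with normal distribution and similar variance will be compared using the t-test, and variables with non-normal distribution using the non-parametric Wilcoxon test".
- **More than two groups:** ANOVA if both checks pass. Otherwise, "For variables with heteroscedastic variances and/or non-normal distribution, the Kruskal-Wallis post hoc test will be applied".
- **Course over time:** repeated-measures ANOVA with intervention type as the main factor, but "In case of non-normality, the non-parametric Friedman test will be applied".

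The rule covers all variables, including the five that section 5.2.2 selects as primary: RVEe, TAPSE/PAPs, pPTT, S' and TAPSE. No default method is named for any of them. Section 5.8.1 plans 54 patients, 18 per arm, for a 15% improvement.

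**The concern.** The analysis of each primary variable is settled only once its data have been tested. A significant pre-test can be chance, and a non-significant one with 18 patients per arm does not confirm an assumption. One primary variable may be judged on means and the next on ranks, and the same variable may be handled differently at T1, T2 and T3.

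The rule is also incomplete:

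- It does not say whether normality is checked by arm, on pooled values or on residuals, or at which time.
- The two-group rule has no branch for normal data with unequal variances.

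Two analysts who follow the text could report different primary tests.

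The temporal analysis matters most. There the switch changes the question as well as the scale, from a comparison by intervention to a test of change over time.

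**Working it through.** **Inputs.** Three arms of 18 (section 5.8.1; 3 × 18 = 54). Five primary variables (section 5.2.2). Significance level 0.05 (section 5.8.2). No separate level is given for the pre-tests, so 0.05 is assumed for them too. The plan gives no figure of its own for this point, so there is none to reproduce.

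**1. Chance switching of a normal, equal-variance variable at one time point**

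- By arm, three Shapiro-Wilk tests: 1 − 0.95³ = 0.143.
- By arm, with Levene added: 1 − 0.95⁴ = 0.185. Simulation (6,000 trials) gives 0.179 or 0.197, depending on whether Levene is centred at the median or the mean.
- One Shapiro-Wilk test on pooled residuals (n = 54) plus Levene: 1 − 0.95² = 0.098. Simulation gives 0.094.

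The range is about 9% to 20%, depending on a choice that the protocol leaves open.

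**2. At least one of five primary variables switched, if independent**

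- At 9%: 1 − 0.91⁵ = 0.38.
- At 18.5%: 1 − 0.815⁵ = 0.64.
- At 19.7%: 1 − 0.803⁵ = 0.67.

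TAPSE is the numerator of TAPSE/PAPs, so independence does not hold fully and these figures are only a guide.

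**3. Cost of the ANOVA/Kruskal-Wallis switch** (6,000 simulated trials per row; two-stage means Kruskal-Wallis if any check by arm fails; power for a shift of 0.95 SD in two arms)

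| Data | Measure | ANOVA | Kruskal-Wallis | Two-stage |
|---|---|---|---|---|
| Normal | Type I error | 0.052 | 0.049 | 0.054 |
| Normal | Power | 0.825 | 0.794 | 0.820 |
| Lognormal, sigma 0.25 | Type I error | 0.050 | 0.047 | 0.050 |
| Lognormal, sigma 0.25 | Power | 0.824 | 0.830 | 0.841 |
| Lognormal, sigma 0.5 | Type I error | 0.046 | 0.051 | 0.053 |
| Lognormal, sigma 0.5 | Power | 0.819 | 0.903 | 0.905 |

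Type I error stays near 0.05. Power is within 0.005 of ANOVA on normal data and higher than ANOVA on skewed data.

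**4. The Friedman branch.** Only the normality check triggers it. With tests by arm and time there are nine Shapiro-Wilk tests per variable. Under independence, 1 − 0.95⁹ = 0.37, and simulation with time correlations of 0.5 to 0.7 gives 36% to 37%.

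Friedman ranks the three time points within each patient, and the patient's arm does not enter the statistic. As a check, 54 patients were simulated with a common rise of 0.5 SD from T1 to T3, time correlation 0.6 and no treatment difference. Friedman rejected in 87% of trials. A between-arm comparison of change rejected in 4% to 4.5%. A significant Friedman result therefore says nothing about treatment.

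**The case against.** The strongest reply is that the rule is written down in advance, largely mechanical, and shown to do no harm to the error rates of the ANOVA/Kruskal-Wallis choice. That stands: how often a switch occurs does not measure harm, and under marked skewness the switch gains power over ANOVA.

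It is also fair that naming a model is commonly left to the SAP, which is not shown. But the protocol does not leave this open. It states a switching rule, and a SAP that named one method would have to override it.

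Some stronger readings that a reader might infer are not supported:

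- **Real skewness is mostly missed.** This holds only for mild skewness. For lognormal data with CV 20%, 30% and 50%, Shapiro-Wilk in a single arm of 18 rejects in about 12%, 22% and 44%. Under tests by arm, however, any one of three arms triggers the switch: 1 − 0.88³ = 32%, 1 − 0.78³ = 53% and 1 − 0.56³ = 82%. At lognormal sigma 0.25 (skewness 0.78), where 42% is detected, ANOVA keeps its type I error.
- **No effect could be set against the planned 15%.** Section 5.8.2 also lists means and standard deviations as descriptive output, so mean changes can still be reported. What may be lost is a test that matches them.
- **All comparison between arms disappears.** Kruskal-Wallis can still compare the arms at each time. What the Friedman branch removes is the analysis of the course over time by arm.
- **The trial is open, which makes the choice worse.** The protocol describes no blinding, but it does not call the trial open either, and a Shapiro-Wilk result does not depend on who knows the allocation.

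**Conclusion.** The point holds in a limited form. Section 5.8.2 lets pre-tests on the trial data select the method, so test and estimand are not fixed for any of the five primary variables. Chance alone switches about 9% to 20% of normal, equal-variance variables at one time point, assuming pre-tests at 0.05 and full arms of 18. A reader might infer that false-positive rates are inflated, but the simulations do not support this for the ANOVA/Kruskal-Wallis choice.

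The consequences are results on different scales and, more seriously, a temporal analysis that may stop addressing treatment. Severity is low and the repair is cheap.

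**What to change.** - Delete the pre-test switching rule in section 5.8.2, including the Friedman fallback.
- Name one between-arm method in advance for each primary variable, for example a linear model of the T3 value with arm as factor.
- If robust standard errors are used, specify HC3 with an F reference. In simulated normal data with 18 per arm, the three-arm test had type I error 0.048 with HC3, against 0.057 with HC1 and 0.067 with HC0, all with an F reference. With a chi-square reference, HC1 gave 0.067 and HC0 0.077.
- Decide on any log transformation before data are seen. The protocol gives no basis for assigning particular variables to a log or raw scale, so the choice needs its own justification.
- Use residual plots for reporting only, and give a rank-based between-arm comparison of every primary variable as a sensitivity analysis.

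The cost is protocol wording and one added sensitivity analysis. A fixed raw-scale model gives up some power if a variable proves markedly skewed (0.819 against 0.905 at lognormal sigma 0.5), which is why the transformation should be considered beforehand.

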5.7.1 Admission Evaluation

Upon admission, patient monitoring and stability will be checked. After routine arterial and venous blood gas extraction, the air test and lung ultrasound will be performed to determine the presence of atelectasis. If the presence of collapse is confirmed, informed consent will be obtained from the family if it has not been given previously. If affirmative, randomization will be conducted, and impedance belts will be placed.

5.7.2 Protocol Measurement Time Points:

T1: Admission

Baseline measurements will be taken upon arrival in the intensive care unit, once the patient has been monitored, postoperative atelectasis has been confirmed (using lung ultrasound or air test), and the patient is in a stable condition after initial laboratory tests.

T2: Baseline

30 minutes after the first measurement under reference ventilation conditions. Depending on the observed response in right ventricular function, the iNO dose will be adjusted. If no improvement is observed, the iNO dose will be increased to 40 ppm.

T3: Final

30 minutes after applying the specific protocol for each group.

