6.1 Use of Inhaled Nitric Oxide (iNO)

1. The use of high and prolonged doses of iNO can be associated with adverse effects such as the formation of methemoglobin and NO₂. Methemoglobin levels above 8-10% can lead to symptoms related to functional anemia, as methemoglobin cannot bind oxygen. NO₂ is a common air pollutant that can be toxic at elevated levels due to the formation of reactive oxidative stress species.

Given the doses used and the duration of use, it is unlikely that elevated levels of both will occur. However, methemoglobin levels will be monitored through two blood gas measurements, one at 30 minutes and another at the end of iNO administration (1 hour). The SoKinox system continuously monitors NO₂ levels in the inspired gas and has safety alarms.

iNO may precipitate or worsen left heart failure in patients with preexisting ventricular dysfunction due to increased left preload. This protocol specifically excludes patients with poor preexisting ventricular function or instability. Cardiac function will be monitored through echocardiography performed at 30 minutes (T2) and immediately after (T3) iNO administration. If there are clear signs of deteriorating left ventricular function (more than 20% drop in LVEF) during the examination compared to the initial function measured upon admission (T1), administration will be stopped.

The following criteria (any of them) will be established for dose reduction or discontinuation of iNO:

- NO₂ levels > 1 ppm
- Methemoglobin fraction > 2.5%
- Variations in inspired oxygen concentration \pm 5% compared to ventilator settings
- Development of left ventricular failure data (drop in LVEF > 20% compared to initial level (T3) in echocardiographic controls.

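### For non-normal data the longitudinal ANOVA is replaced by the Friedman test, which has no arm term; the baseline labels for T1 and T2 also need reconciling

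*Protocol*

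**What the plan says.** Protocol section 5.8.2 gives two sets of methods for continuous variables in the three arms.

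- **Comparing arms.** ANOVA with post hoc tests when assumptions hold. Otherwise: "For variables with heteroscedastic variances and/or non-normal distribution, the Kruskal-Wallis post hoc test will be applied".
- **Change over time.** "To analyze temporal evolution, a repeated measures ANOVA will be used with the intervention type as the main factor". The next sentence gives the substitute: "In case of non-normality, the non-parametric Friedman test will be applied". It does not say whether Friedman is run on all 54 patients together or arm by arm.

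The time points are defined in section 5.7.2. Under the T1 (Admission) heading: "Baseline measurements will be taken upon arrival in the intensive care unit". The next time point, T2, is itself headed Baseline and is taken "30 minutes after the first measurement under reference ventilation conditions". The same entry adds: "Depending on the observed response in right ventricular function, the iNO dose will be adjusted". Sections 5.3.1 and 5.7 start iNO directly after randomization, and section 6.1 says: "Cardiac function will be monitored through echocardiography performed at 30 minutes (T2) and immediately after (T3) iNO administration".

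**The concern.** The repeated-measures ANOVA can show whether the arms evolve differently. Its replacement can show only whether patients change over time. A normality test on the data would therefore change the question as well as the method. A significant Friedman result for a non-normal variable could be reported as an effect of the intervention when it shows only that patients changed after surgery. A real difference between arms could equally leave no trace in it. Change shared by all arms is plausible here, because the intervention period is the first two to three postoperative hours (section 5.1).

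The second matter is which measurement is the reference. Both T1 and T2 carry the word baseline, and T2 is taken on drug in two of the three arms.

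**Working it through.** **Inputs from the protocol.** Three arms (5.7); 54 patients, 18 per arm (5.8.1); three time points (5.7.2); significance level 0.05 (5.8.2). Section 5.8.1 assumes a 15% improvement but gives no SD, correlation, drift or power. There is thus no figure of the plan's own to reproduce on this point.

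**Structure (no assumptions needed).** With N patients and k = 3 time points, let R_j be the sum over patients of the within-patient rank at time j. Then

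Q = 12/(N·k·(k+1)) · ΣR_j² − 3N(k+1) = (1/N)·ΣR_j² − 12N,

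referred to chi-square with 2 df. The arm does not enter. As a check, reassigning patients to arms in one simulated data set of 54 left the statistic at 0.778 (p = 0.678) both times. Because only within-patient ranks are used, a monotone transformation of the data, such as from normal to lognormal, changes no result.

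**Illustration.** Assumed: unit SD, equal correlation rho between time points, 20,000 simulated trials. Shared drift is 0, d/2, d at T1, T2, T3 in every arm, with no arm effect. Entries are the proportion significant at rho 0.3/0.5/0.7.

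| Analysis | d = 0.2 SD | d = 0.5 SD |
|---|---|---|
| Friedman pooled, n = 54 | 14/19/27% | 64/79/95% |
| Friedman within one arm, n = 18 | 7/8/11% | 23/31/49% |
| Friedman significant in iNO, not in CONT | 6/8/10% | 18/21/25% |
| Group-by-time ANOVA | about 5% | about 5% |

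With no drift, pooled Friedman is at 5%.

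- *True effect* (CONT flat, both iNO arms +0.96 SD at T2 and T3): pooled Friedman rejects in 92/98/100%. A significant result does not separate this from drift.
- *Diverging arms* (CONT −0.5, iNO 0, iNO-RM +0.5 SD at T3, half of that at T2): pooled Friedman rejects in 4 to 5%. At an assumed rho of 0.6, Kruskal-Wallis rejects in 70% on the T3 value and 78% on the change from T1 to T3.

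**What adjusting for T1 would add.** Two arms of 18, two-sided 0.05, assumed difference 0.961 SD. This value is not in the protocol; it is the difference that a T3-only comparison detects with 80% power.

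- T3 alone: noncentrality 0.961·√(18/2) = 2.883, df 34, power 80%.
- ANCOVA on T1: noncentrality 2.883/√(1−rho²) = 3.02/3.33/4.04, df 33, power 83/90/97%.
- Group-by-time ANOVA, effect 0, 0.96, 0.96 SD (simulated): about 69/84/97%.
- Rank-based (simulated): Kruskal-Wallis at T3 78%; rank ANCOVA 80/87/95%.

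The gain from ANCOVA over the planned ANOVA is about 14, 6 and 0 percentage points.

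**The labels side by side.**

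| Section | T1 | T2 | T3 |
|---|---|---|---|
| 5.7.2 | headed Admission, described as baseline | headed Baseline; iNO dose adjusted on response | headed Final |
| 6.1, monitoring text | initial function | 30 minutes of iNO | end of iNO |
| 6.1, list of criteria | – | – | named as initial level for the LVEF drop |

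Section 6.1 first sets the LVEF comparison against admission, "compared to the initial function measured upon admission (T1"), and its list of criteria then cites T3 as the initial level.

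**The case against.** The strongest reply is that section 5.8.2 divides the work: arms by ANOVA or Kruskal-Wallis, time by Friedman. Friedman is assigned to temporal evolution and nothing says it will be read as evidence of an intervention effect. Whether it is pooled or run by arm is detail that an analysis plan may settle.

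Part of this stands. A reader might infer that non-normal outcomes have no between-arm test and that the primary aim goes untested. The text does not support that, because Kruskal-Wallis remains. A reader might also take 64/79/95% as the trial's false-positive rate. It is not. It needs a pooled test, which the protocol does not specify; an assumed drift; and a report that calls a time effect an arm effect.

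What does not stand is that the choice is mere detail. The ANOVA for temporal evolution has the intervention as its main factor, and the named substitute loses it however it is run.

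Two further inferences go too far. One is a large loss of precision from not adjusting for T1: that appears only against T3 alone and shrinks to nothing against the planned ANOVA at rho 0.7. The other is that T2 will be subtracted as the baseline and cancel the early iNO effect. With assumed effects of 0.8 SD at T2 and 0.9 SD at T3, a change from T2 would indeed recover only 0.10 SD, but no planned test takes T2 as its reference. The T2 label may refer to ventilation: sections 5.3.2 and 5.5.1 use baseline for ventilator settings, and the T2 entry speaks of reference ventilation. Figure 1 is not shown and may make this clear.

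**Conclusion.** The point holds within limits and should be fixed. As written, the fallback cannot do the job of the analysis that it replaces. This follows from the form of the Friedman statistic and rests on no assumed number. It affects only the longitudinal analysis, and only variables judged non-normal. The consequence is a risk of misreading and a missing arm-by-time comparison for those variables. The simulated rates show direction and possible size under assumed SD, correlation and drift.

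Adjusting for T1 is an improvement at no cost; leaving it out is not an error. The label conflict is real, since T2 is on iNO in two arms, but it changes no stated test. It is a matter of reconciling sections 5.7.2 and 6.1.

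**What to change.** 1. In section 5.8.2, keep the intervention in the longitudinal analysis of non-normal variables. Options are a mixed model on transformed data with arm, time and arm-by-time, or rank ANCOVA of the post-treatment value on arm and the T1 value. Kruskal-Wallis at T3 can serve as the simple fallback.
2. Limit Friedman to describing change within an arm, and state that it is not evidence of a difference between arms.
3. In section 5.7.2, name T1 as the pre-treatment baseline for the analysis. Describe T2 as a measurement under reference ventilation that is on treatment in the two iNO arms.
4. Reconcile the two statements in section 6.1 on the initial level for the LVEF comparison. Which time point should govern that clinical rule is for the investigators to decide; this review takes no position on it.

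The cost is wording only, with no new measurements, visits or patients, because T1 is already collected.

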6.1 Use of Inhaled Nitric Oxide (iNO)

1. The use of high and prolonged doses of iNO can be associated with adverse effects such as the formation of methemoglobin and NO₂. Methemoglobin levels above 8-10% can lead to symptoms related to functional anemia, as methemoglobin cannot bind oxygen. NO₂ is a common air pollutant that can be toxic at elevated levels due to the formation of reactive oxidative stress species.

Given the doses used and the duration of use, it is unlikely that elevated levels of both will occur. However, methemoglobin levels will be monitored through two blood gas measurements, one at 30 minutes and another at the end of iNO administration (1 hour). The SoKinox system continuously monitors NO₂ levels in the inspired gas and has safety alarms.

iNO may precipitate or worsen left heart failure in patients with preexisting ventricular dysfunction due to increased left preload. This protocol specifically excludes patients with poor preexisting ventricular function or instability. Cardiac function will be monitored through echocardiography performed at 30 minutes (T2) and immediately after (T3) iNO administration. If there are clear signs of deteriorating left ventricular function (more than 20% drop in LVEF) during the examination compared to the initial function measured upon admission (T1), administration will be stopped.

The following criteria (any of them) will be established for dose reduction or discontinuation of iNO:

- NO₂ levels > 1 ppm
- Methemoglobin fraction > 2.5%
- Variations in inspired oxygen concentration \pm 5% compared to ventilator settings
- Development of left ventricular failure data (drop in LVEF > 20% compared to initial level (T3) in echocardiographic controls.

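### Section 6.1 takes the LVEF rule for stopping iNO against admission (T1) in one place and the final echo (T3) in another, and does not settle whether iNO is still running at T3

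*Protocol*

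**What the plan says.** All references are to the protocol.

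- **6.1, prose on the left ventricle.** "Cardiac function will be monitored through echocardiography performed at 30 minutes (T2) and immediately after (T3) iNO administration". If LVEF falls by more than 20% "compared to the initial function measured upon admission (T1), administration will be stopped".
- **6.1, criteria list.** It opens with "The following criteria (any of them) will be established for dose reduction or discontinuation of iNO". Its last item is a "drop in LVEF > 20% compared to initial level (T3) in echocardiographic controls".
- **5.7.2, measurement times.** T1 is labelled admission, T2 baseline and T3 final. T3 is taken "30 minutes after applying the specific protocol for each group". Nothing is said about whether iNO is on or off at that moment.
- **5.3.1 and 5.7.2, dose step.** After 30 minutes at 20 ppm the dose may rise. 5.7.2 puts it as "If no improvement is observed, the iNO dose will be increased to 40 ppm"; 5.3.1 allows the step only if methemoglobin is not above 2.5%.
- **6.1, methemoglobin.** "methemoglobin levels will be monitored through two blood gas measurements, one at 30 minutes and another at the end of iNO administration (1 hour". The stated reasoning is "Given the doses used and the duration of use, it is unlikely that elevated levels of both will occur".
- **Section 3.** The primary aim is the effect of iNO on pulmonary vascular mechanics, right ventricular function and their coupling.

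**The concern.** The criteria list is the part of 6.1 that staff will apply at the bedside when deciding whether to reduce or stop iNO. One of its four items is measured against the last examination of the study, which cannot serve as a starting value. The sentence above it uses a different reference for the same 20% threshold. The rule has a purpose: 6.1 itself warns that iNO can worsen left heart failure, and Section 4 admits preoperative LVEF down to 30%.

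The placing of the T3 echo raises a second question. If the echo follows the end of iNO, nothing is left to stop on its result. If iNO is meant to be running, 6.1 does not say so. This reaches beyond safety, because T3 supplies the final reading of the iNO effect. On-drug and off-drug readings are different measurements, and the text gives the two centres no common instruction.

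**Working it through.** **1. The timeline (reproduces the plan's 1 hour).** Inputs: iNO starts after the T1 data collection (5.7); T2 and the dose decision come 30 minutes later (5.3.1, 5.7.2); T3 comes 30 minutes after the group protocol is applied (5.7.2); iNO ends at 1 hour (6.1).

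- Start of iNO = 0 min; T2 = 30 min.
- T3 = 30 + 30 = 60 min.
- End of iNO = 1 hour = 60 min.

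The two sections agree on clock time. Counting the 30 minutes of T3 from the start of iNO instead would give T3 = 30 min = T2, which is impossible for two separate time points.

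**2. The LVEF criterion under each reference.** Fall = LVEF at reference minus LVEF at the current echo.

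| Current echo | Reference T3 (criteria list) | Reference T1 (prose) |
|---|---|---|
| T2 (30 min) | reference not yet measured | can be computed |
| T3 (60 min) | LVEF(T3) − LVEF(T3) = 0, never above 20% | can be computed |
| Usable echoes | 0 of 2 | 2 of 2 |

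**3. The drug state at T3, statements side by side.**

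- 6.1 places the T3 echo after iNO administration: iNO is off.
- 6.1, next in the same paragraph, stops administration if the examination shows a fall: iNO is on.
- 5.7.2 gives only the time since the group protocol was applied: no information.

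If iNO is off at T3, only the T2 echo can trigger a stop (1 of 2). If it is on, T3 still falls at the planned end, so the time saved by stopping is about 60 − 60 = 0 min. Settling the drug state makes the rule coherent and defines the final measurement; it does not bring earlier action on LVEF.

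**4. Patients affected.** Two arms receive iNO, with 18 patients each (5.8.1): 2 × 18 = 36 of 54.

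**5. Methemoglobin.** Scheduled gases fall at 30 and 60 min. The 40 ppm period, where used, runs from 30 to 60 min and lasts 60 − 30 = 30 min. Scheduled gases strictly inside it: 0. The protocol gives neither the chance nor the time of crossing 2.5%, so how much an extra gas would gain cannot be calculated from it.

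**The case against.** The strongest reply on LVEF is that the list contains a labelling slip. The prose just above names T1 with the same threshold, the bullet itself speaks of an initial level, and 5.7.2 labels T3 as final. A cardiologist reading all of 6.1 would use T1. This stands in part: a reader might infer that the protocol has no workable LVEF rule, and that would be wrong, because the prose supplies one. The 0 of 2 describes the bullet taken alone. The slip still sits in the operative list and should not be left for staff to interpret.

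On T3, a reader might infer that 6.1 schedules the echo at the wrong time. The documents do not support that. Both sections put T3 at about 60 minutes, and Figure 1, the study scheme, is not available here. The intent may well be an on-drug echo. What remains is that the text does not say so and that 6.1 points both ways. That the centres would in fact differ is a possibility, not something the protocol shows.

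On methemoglobin, a reader might infer that monitoring at 40 ppm is inadequate and that another gas is required. That goes too far. The step is gated at 2.5%, the 40 ppm exposure is about 30 minutes, and 6.1 gives its reason for expecting no raised levels. It also places symptoms at 8–10%, well above the action limit. The criterion can act at 30 minutes, the end gas would record a late rise, and nothing forbids an unscheduled sample.

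**Conclusion.** Section 6.1 is wrong as written on one point and unclear on another.

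- **Wrong:** the LVEF reference in the criteria list. Taken alone, the bullet can be applied at 0 of 2 follow-up echoes; with the T1 reference of the prose, at 2 of 2. This is a contradiction inside a safety rule, not the absence of a rule.
- **Unclear:** whether iNO is running at T3, the final measurement for the primary aim. This concerns up to 36 of 54 patients. A timing error is not established.

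The absence of a scheduled methemoglobin gas within the 40 ppm period is a fact worth noting, but it is a choice for which the protocol gives a reason, not an error.

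The conclusion on the reference rests on the text alone. The timeline assumes that the 30 minutes to T3 run from the T2 adjustment, the only workable reading found. If Figure 1 shows iNO running at T3, the intent is clear, but the wording of 6.1 still has to be brought into line.

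**What to change.** 1. In the last item of the criteria list in 6.1, change (T3) to (T1).
2. In the prose of 6.1, replace the wording that places T3 after iNO with a statement that the T3 echo is taken at the end of the iNO period, before iNO is switched off. Repeating this in the T3 entry of 5.7.2 would keep the two sections aligned.

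Both changes are wording only. They add no echo, sample, visit or staff time, and leave the sample size and schedule untouched.

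Optional, for the sponsor's clinicians to decide: one methemoglobin gas partway through the 40 ppm period in patients who are stepped up. This would cost one small extra sample in at most 36 patients. The point does not depend on it.

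### Section 6.1 gives the LVEF rule for iNO twice, with different reference time points (T1 and T3) and different actions (stop, or reduce or stop)

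*Protocol*

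**What the plan says.** Section 6.1 acknowledges that iNO may bring on or aggravate left heart failure and sets an LVEF rule against that risk. The rule appears twice.

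- **Running text.** The trigger is "If there are clear signs of deteriorating left ventricular function (more than 20% drop in LVEF"), and the reference and action follow: "compared to the initial function measured upon admission (T1), administration will be stopped".
- **Criteria list.** The header says that meeting any one of the criteria "will be established for dose reduction or discontinuation of iNO". The fourth item is the LVEF criterion: "drop in LVEF > 20% compared to initial level (T3) in echocardiographic controls".

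The same section schedules "echocardiography performed at 30 minutes (T2) and immediately after (T3) iNO administration". It times the two methemoglobin samples as "one at 30 minutes and another at the end of iNO administration (1 hour"), which fixes the planned course of iNO at one hour.

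Section 5.7.2 defines the time points. T1 is Admission: "Baseline measurements will be taken upon arrival in the intensive care unit". T3 is Final: "30 minutes after applying the specific protocol for each group".

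**The concern.** The two statements share the 20% threshold but differ in the reference value and in what must be done when the threshold is crossed. Nothing in the protocol says which one governs.

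The reference in the list contradicts itself, because the final measurement cannot be the initial level. A reader who knows the schedule will recognise the slip. The action is harder to resolve by inspection. A centre working from the list could lower the dose and continue iNO in a patient for whom the text requires it to be stopped, and a monitor could not say whether that was compliance or a deviation. The trial runs at two centres and admits patients with a preoperative LVEF as low as 30% (section 4), so this rule should have one reading.

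**Working it through.** No stated figure needs reproducing. The check sets the two statements beside the schedule.

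| Element | Text of 6.1 | List in 6.1 | Agree? |
|---|---|---|---|
| Threshold | LVEF drop of more than 20% | LVEF drop of more than 20% | Yes |
| Reference | Admission, T1 | Initial level, labelled T3 | No |
| Action | Stop | Reduce dose or stop | No |

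**Reference.** Take the list literally, with T3 as the reference, and apply it at each safety scan.

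- At T2 no T3 value exists yet, so the criterion cannot be evaluated. T2 is the only scheduled scan during administration.
- At T3 the comparison is LVEF(T3) − LVEF(T3) = 0, so a drop above 20% can never be found.

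As printed, the list criterion can never trigger. With T1 in place of T3 it works at both scans and matches the text.

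**Action.** Inputs, all from section 6.1: planned iNO duration 60 minutes, T2 at 30 minutes, T3 immediately after iNO ends.

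- Time remaining after T2: 60 − 30 = 30 minutes.
- Share of the planned course: 30 / 60 = 50%.
- Text, drop found at T2: 0 further minutes.
- List, dose reduction chosen at T2: up to 30 further minutes at a reduced dose.
- Drop found at T3: iNO has already ended, so the two actions do not differ.

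The two versions therefore diverge in practice only at T2.

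**Dose at T2.** Under sections 5.3.1 and 5.7, iNO starts at 20 ppm and may rise to 40 ppm only after the 30-minute assessment. A reduction at T2 therefore means a dose below 20 ppm, and the protocol specifies none. Of the safety measures, the escalation condition in 5.3.1 names only methemoglobin, so the LVEF rule in 6.1 is the stated left-ventricular safeguard at that assessment.

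**Scope.** Two of the three arms receive iNO, so the rule governs 2 × 18 = 36 of the 54 planned patients. The protocol does not say how many might have a qualifying drop, and none is assumed here.

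**The case against.** The strongest reply is that this is a matter for proofreading. The word initial in the list, the paragraph just above it and the names of the time points all point to T1. The parenthesis in the list item is not closed, so the T3 label may even be a misplaced tag for the follow-up scan. On the action, the header covers four criteria (NO₂, methemoglobin, inspired oxygen and LVEF) and may only name the set of possible responses. The specific sentence in the text would then govern, and stopping satisfies both versions. Finally, since the patient is still on 20 ppm at T2, the lowest dose the protocol gives, a reduction at that point has no defined meaning.

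Much of this stands. The label is easily recognised as a slip, the safeguard in the text still works, and a careful reader can comply with both versions by stopping. It does not remove the inconsistency. The header applies to any of the four criteria without exception, so it permits reducing and continuing where the text does not. The absence of a defined dose below 20 ppm makes that option less clear, but does not withdraw it. The misplaced-tag reading cannot be shown from the document and would leave the difference in action untouched.

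**Conclusion.** The concern holds and is minor. One bedside safety rule is written with two references, one of them impossible under the protocol's own schedule, and with two actions. The practical difference is bounded: it arises only for a patient with a qualifying drop at T2, and it amounts to at most 30 minutes of further iNO, half the planned course, at an undefined reduced dose. That bound assumes the one-hour course and the scan times given in section 6.1, and that a centre reads the header as applying to the LVEF item. The number of patients concerned cannot be derived from the protocol. Sample size, error rates and the efficacy analysis are unaffected.

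**What to change.** In the LVEF item of the section 6.1 list, replace T3 with T1 and state that for this criterion iNO is stopped, as the text already requires. The shared header can stay for the other three criteria.

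The cost is a wording correction to one list item. No measurement is added, because the rule in the text already relies on LVEF at T1 and on the T2 and T3 scans.
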